#### 3.3.2. Secondary outcomes

- Absolute FVC, measured in millilitres (ml) will be recorded using the pulmonary function test (PFT) at 12 weeks post-randomisation, and used to calculate change in absolute FVC between baseline and 12-weeks post-randomisation.
- 2. Percentage change in FVC will be calculated (using the absolute FVC values collected at baseline, 12 and 26 weeks post-randomisation) between (i) baseline and 12 weeks and (ii) baseline and 26 weeks post-randomisation.
- Absolute change in percentage predicted FVC will be calculated between (i) baseline and 12 weeks and (ii) baseline and 26 weeks post-randomisation, using percentage predicted FVC calculated centrally by ExeCTU using Global Lung Initiative (GLI) reference equation.
- 4. Absolute DLco, measured in mmol min kPa, will be recorded using the European Respiratory Society (ERS) guidelines, at baseline and 26-weeks post-randomisation and used to calculate change in absolute DLco between baseline and 26 weeks post-randomisation.
- 5. Percentage change in DLco will be calculated (using the absolute DLco values collected at baseline and 26 weeks post-randomisation) between baseline and 26 weeks post-randomisation.
- 6. Absolute change in percentage predicted DLco will be calculated between baseline and 26 weeks post-randomisation.
- 7. Initiation of antifibrotic therapy given by 26 weeks post randomisation.
- 8. Additional immunosuppressant therapy given by 26-weeks post-randomisation.
- 9. Quality of life will be measured at baseline, 12 and 26 weeks post-randomisation. Changes in quality of life from (i) baseline to week 12 and (ii) baseline to week 26 will be measured using
  - L-PF questionnaire [22] (dyspnoea, cough and fatigue domain scores of principal interest)
  - PGI-S scale [23]
  - the cough VAS [24]
  - EQ-5D-5L Visual Analogue Scale [25]
- 10. Safety data will be collected in accordance with MedDRA and defined as the number and proportion of participants experiencing Serious Adverse Events (SAEs) and

related Adverse Events (AEs) throughout the duration of the trial. Specific events of interest are:

- o adverse reactions
- o respiratory hospitalisations
- o acute exacerbations
- weight gain/increased waist circumference (percentage change)
- o adverse events of special interest- infections (listed in section 9.3)
- o death

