#### 8.7. Dosage modifications

This trial has been designed to mimic clinical practice wherever possible and it is anticipated that investigators may want to increase the IMP for short periods of time based on clinical events, such as 1. Intercurrent infections/exacerbations or 2. perceived respiratory deteriorations (symptomatically) on dose titration from 40mg to 10mg. Or investigators may want to dose reduce from 40mg to 10mg at faster rate than outlined in section 8.6.1 for example if the participant experiences significant psychiatric events believed to be related to higher doses of prednisolone.

Participants have been provided with additional IMP to allow a short-term increase in IMP to occur in a blinded fashion. While the final decision on dosage will be left to discretion of the treating local investigators, we would recommend the following:

- 1. For intercurrent infections/exacerbations: a standard escalation to 6 capsules (30mg) for 7 days, with reduction thereafter back to previous dose of IMP
- 2. For perceived deteriorations in symptoms during the titration period (Days 0 to 70) then the local investigator may increase the IMP to the last previously effective dose for 7 days, then reattempt a further wean down to the planned dosing schedule.

If the dose modifications are not successful then the local investigator should contact the trials team to discuss the appropriate next steps.

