#### 9. PHARMACOVIGILANCE

#### 9.1. Definitions

#### Table 4: Adverse event definitions

Term	Definition
Adverse Event (AE)	Any untoward medical occurrence in a participant to whom a medicinal product has been administered, including occurrences which are not necessarily caused by or related to that product.
Adverse Reaction (AR)	An untoward and unintended response in a participant to an investigational medicinal product which is related to any dose administered to that participant.
	The phrase "response to an investigational medicinal product" means that a causal relationship between a trial medication and an AE is at least a reasonable possibility, i.e. the relationship cannot be ruled out.
	All cases judged by either the reporting medically qualified professional or the Sponsor as having a reasonable suspected causal relationship to the trial medication qualify as adverse reactions. It is important to note that this is entirely separate to the known side effects listed in the SmPC. It is specifically a temporal relationship between taking the drug, the half-life, and

	the time of the event or any valid alternative aetiology that would explain the event.		
Serious Adverse Event (SAE)	A serious adverse event is any untoward medical occurrence that:		
	
 
results in death
 
is life-threatening
 
requires inpatient hospitalisation or prolongation of existing hospitalisation
 
results in persistent or significant disability/incapacity
 
consists of a congenital anomaly or birth defect
 
		
	In addition for this trial		
	
 
acute respiratory exacerbations that require attendance to accident and emergency (A&E) will be reported as an SAE
 
		
	Other 'important medical events' may also be considered serious if they jeopardise the participant or require an intervention to prevent one of the above consequences.		
	NOTE: The term "life-threatening" in the definition of "serious" refers to an event in which the participant was at risk of death at the time of the event; it does not refer to an event which hypothetically might have caused death if it were more severe.		
Serious Adverse Reaction (SAR)	An adverse event that is both serious and, in the opinion of the reporting Investigator, believed with reasonable probability to be due to one of the trial treatments, based on the information provided.		

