#### 9.3. Recording and reporting of Adverse events (AEs)

The safety reporting period will begin from the time of randomisation up to the week 35, End of Study telephone follow-up. The recording and reporting requirements are summarised in the safety reporting flowchart in Figure 5. Adverse events should be reviewed at every follow up visit.

Figure 5: Safety reporting flow chart

All adverse events will be assessed for seriousness and causality as per the definitions in section 9.1 above. These assessments should be carried out by the site PI, or delegated medically qualified doctor, and recorded in the medical notes. If the adverse event is possibly, probably or definitely related to prednisolone it is considered an adverse reaction (AR) and must be reported in the adverse event eCRF in REDCap. In addition to this any viral, fungal or bacterial infections of any kind are considered Adverse Events of Special Interest (AESI) for this trial and must be reported on the adverse event eCRF. If the adverse event doesn't meet the definition of serious and is not considered to be an AESI or AR it should only be documented in the participants medical notes but not be reported on the adverse event eCRF.

All related and unrelated adverse events that are considered serious, as defined in section 9.1, must be reported as an SAE. Additional guidance for reporting serious adverse events can be found in section 9.4 below.

As this is a blinded trial, adverse events should be evaluated on the assumption that the participant was allocated the active drug i.e. prednisolone. The blind should only be broken where knowing the allocation is clearly necessary and will alter the appropriate medical management of the participant. If unblinding is necessary, please refer to the Emergency Unblinding section of the protocol (7.7.1) and the CHORUS 'Unblinding' working instruction.

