#### 10.10. Primary analysis of secondary outcomes

Secondary outcomes will be reported descriptively at each timepoint collected. Analysis of secondary outcomes, including the PROMS, will use similar mixed-effects models, with adjustments for baseline outcome where relevant, maximising the use of longitudinal data where possible. Binary outcomes (initiation of anti-fibrotic medication/additional immunosuppressive therapy; hospitalisations/acute exacerbations/death) will be analysed using logistic regression and time to event analyses, with adjustments in the models as per the primary analyses. Secondary outcomes assessing safety, such as related adverse events and serious adverse events, will be descriptively summarised only.

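### Acute exacerbations are a listed safety event with planned logistic and time-to-event analyses, but section 9.3 keeps non-infective, unrelated, non-serious exacerbations off the adverse event eCRF

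*Protocol*

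**What the plan says.** Protocol section 3.3.2, outcome 10, lists "acute exacerbations" as one of the safety events of particular interest, separately from adverse reactions, respiratory hospitalisations, infections and death. The parent outcome is "defined as the number and proportion of participants experiencing Serious Adverse Events (SAEs) and" related adverse events.

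Section 10.10 names exacerbations among the binary outcomes: "hospitalisations/acute exacerbations/death) will be analysed using logistic regression and time to event analyses". The same paragraph ends: "Secondary outcomes assessing safety, such as related adverse events and serious adverse events, will be descriptively summarised only".

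Section 9.3 decides what sites enter. Serious events go on the SAE eCRF. Adverse reactions (at least possibly related) and infections, the only adverse events of special interest (AESIs), go on the adverse event eCRF. For everything else, "it should only be documented in the participants medical notes but not be reported on the adverse event eCRF".

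Table 4 (section 9.1) widens the definition of a serious event to include "acute respiratory exacerbations that require attendance to accident and emergency". Section 8.7 anticipates exacerbations during treatment and gives a recommendation on the trial drug for them: "For intercurrent infections/exacerbations: a standard escalation to 6 capsules (30mg) for 7 days".

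Table 2 schedules an adverse event review at weeks 4, 8, 12, 26 and 35. It has no item for exacerbations, and no exacerbation form is named elsewhere. The text shown does not define acute exacerbation.

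**The concern.** The analysis section and the recording section do not cover the same events. Section 10.10 models acute exacerbations without limiting them to serious, related or infective ones. Section 9.3 tells sites not to enter those that are none of these.

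Two things are at stake. First, the label on the result would not match what was counted. Whether a milder, non-infective exacerbation enters the data depends on the local causality opinion and on whether the participant went to A&E or was admitted. Second, a time-to-event analysis needs a date for every event, and an event that stays in the medical notes supplies none. A SAP can restrict the outcome to what was collected, but it cannot analyse events that sites were told not to enter. Later retrieval would mean searching notes at about 30 sites (section 10.2).

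**Working it through.** There is no plan figure to reproduce: the protocol gives no exacerbation rate, and the sample size in section 10.1 rests on FVC alone. The main check is a trace of each kind of exacerbation through the recording rules.

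| Kind of exacerbation | Route | Source |
|---|---|---|
| Admission, A&E attendance or another seriousness criterion | SAE eCRF, whatever the cause | Table 4, 9.4 |
| Infective, not serious, unrelated | Adverse event eCRF, as an infection AESI | 9.3 |
| At least possibly related, not serious | Adverse event eCRF, as an adverse reaction | 9.3 |
| Non-infective, judged unrelated, not serious | Medical notes only | 9.3 |

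Only the last row has no event route. Could other forms fill the gap?

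- **Dose-modification eCRF (8.11).** It records changes of trial drug advised by the clinical team. The protocol does not say that it codes the reason, and Table 2 schedules it only at weeks 12 and 26.
- **Concomitant-medication eCRF (8.9).** It records medicines. An exacerbation handled only with trial capsules the participant already holds need not add one.
- **Onset date.** Section 9.4 lists it among the SAE items. No corresponding item is stated for an event kept in the notes.

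Neither form is therefore stated to give a diagnosis and an onset date. Because section 8.7 foresees exacerbations met by a change of trial drug, the last row need not be empty. Its size cannot be derived from the protocol.

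**Illustration only.** All risks and capture shares here are assumptions. Take n = 111 per arm (222/2, before the planned 10% loss), a two-sided 5% level, true 26-week risks p1 and p2, and the same captured share s in both arms, so that the recorded risks are s·p1 and s·p2. With d the difference and p̄ the mean of the recorded risks:

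power = Φ[(d − 1.96·SE0)/SE1], where SE0 = √(2p̄(1−p̄)/n) and SE1 = √((p1(1−p1)+p2(1−p2))/n), using the recorded risks throughout.

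- Full capture, 20% v 10%: SE0 = √(2×0.15×0.85/111) = 0.0479; SE1 = √((0.16+0.09)/111) = 0.0475; power = Φ[(0.10 − 0.0939)/0.0475] = Φ(0.13) = 55%.
- Half capture, 10% v 5%: SE0 = √(2×0.075×0.925/111) = 0.0354; SE1 = √((0.09+0.0475)/111) = 0.0352; power = Φ[(0.05 − 0.0693)/0.0352] = Φ(−0.55) = 29%.

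| Assumed true risks | s = 100% | 75% | 50% | 25% |
|---|---|---|---|---|
| 10% v 5% | 29% | 23% | 16% | 10% |
| 20% v 10% | 55% | 42% | 29% | 16% |
| 30% v 15% | 77% | 61% | 42% | 23% |

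For 20% v 10%, the expected counts fall from 22.2 v 11.1 at full capture to 11.1 v 5.6 at half.

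**The case against.** The strongest reply concerns scope. Outcome 10 is headed as serious and related adverse events, and exacerbations are listed beneath it. Read that way, section 9.3 collects at least what the outcome asks for and nothing is lost. The A&E clause in Table 4 shows that the authors did consider a threshold for this event. This has force: a reader might infer that exacerbations are certainly under-counted, and the protocol does not support that, because the intended scope is unsettled. The heading does not settle it either way. Infections sit in the same list and are collected even when neither serious nor related, and exacerbations are listed apart from both adverse reactions and respiratory hospitalisations.

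Other points also stand:

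- A reader might infer that all non-serious, unrelated exacerbations are missing from the database. Infective ones are reported as AESIs, and the rule covers the adverse event eCRF, not every form.
- A reader might take section 8.7 to mean management in the community. It says nothing about place of care.
- The causality bar is low (possibly related is enough) and events are judged as if the participant were on prednisolone, which favours reporting.
- A reader might infer bias between arms. With no true effect and a 20% risk in each arm, capture of 60% v 50% would give recorded risks of 12% v 10% and an odds ratio of (0.12/0.88)/(0.10/0.90) = 1.23. Nothing in the protocol shows unequal capture, and causality is assessed blind.
- The comparison is not powered in any case. Even full capture gives only 29% to 77% in the illustration.
- Figure 5 (the safety reporting flow chart), the safety work instruction and the SAP are not shown and may add detail.

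None of this supplies a stated event record for the last row of the trace.

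**Conclusion.** The point holds in a limited form. Sections 3.3.2 and 10.10 treat acute exacerbation as an outcome to be modelled, while section 9.3 leaves one class of exacerbation without a stated event record or date. What can be analysed is serious, infective or possibly drug-related exacerbation.

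If the intended outcome is all acute exacerbations, events and precision are lost wherever that class is not empty. How much is unknown, and the power table shows only how the loss would scale under assumed rates. If a restricted outcome is intended, the fault is that the protocol neither says so nor defines the event. Either way the passages need reconciling. This is an inexpensive improvement to a secondary safety outcome. The primary FVC analysis is not affected.

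**What to change.** 1. Define acute exacerbation in the protocol.
2. In section 9.3, make acute respiratory exacerbation an AESI, reported on the adverse event eCRF with an onset date whatever its seriousness or causality. The reviews at weeks 4, 8, 12, 26 and 35 already provide the occasion.
3. Reconcile sections 3.3.2, 9.3 and 10.10, including whether exacerbations are modelled or, as the last sentence of 10.10 says of safety outcomes, only described.
4. If a restricted outcome is intended, replace step 2 with a statement in 3.3.2 and 10.10 that it covers only serious, related or infective exacerbations.

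The cost of the first route is a definition, a sentence in 9.3, an eCRF item and slight extra data entry at sites. It changes what is recorded and leaves clinical management as it is. The second route costs only wording, but accepts a narrower outcome.

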### 9.4. Recording and reporting Serious adverse events (SAEs, SARs, SUSARs)

All related and unrelated adverse events that meet the protocol definition

of serious must be reported to ExeCTU

within 24 hours of the PI, delegate or research team becoming aware

by completing the 'SAE' eCRF in REDCap.

All SAE eCRFs must be reviewed and signed off by a PI or delegated medically qualified doctor, within REDCap. In the event of a death, the Death eCRF should be completed *in addition* to the SAE eCRF in REDCap. Any information not available at the time of the initial report (e.g. test results) must be added to the SAE eCRF by the site team as soon as it becomes available.

For each SAE the following information will be collected:

- Full details in medical terms with a diagnosis (if available)
- Event duration (date of onset and date of resolution)
- Reason for seriousness
- Trial drug details
- Action taken
- SAE outcome
- Causality and severity, in the opinion of PI (or medical delegate)

ExeCTU will receive an automated email notification to alert them to a new SAE eCRF or when a change is made to an existing SAE eCRF. In the event of a SUSAR the site will be contacted by the CHORUS trial manager and it may be requested that further details are added SAE eCRF please refer to safety work instruction.

#### 9.4.1. Reviewing serious adverse events

The CI or designated representative will review all reported SAEs to assess causality. Where in either the opinion of the PI and/or CI the SAE is considered possibly, probably or definitely related to the IMP, an assess expectedness to the IMP will be made prednisolone SmPC which serves as the Reference Safety Information (RSI) for the trial. The CI will not downgrade a PI's assessment of causality; however, they may upgrade a PI's assessment of causality (i.e. from unrelated to related).

Sites should respond as soon as possible to requests for further information by the CI or designated representative required for the final assessment of the SAE.

In the event of a SUSAR, ExeCTU will take responsibility for unblinding prior to submission of the SUSAR to the MHRA and the REC. Local investigators will only receive information on the results of the unblinding if it is judged necessary for the safety of the participant. ExeCTU will onward report SUSARs to the Sponsor within 24 hours of becoming aware but all other SAEs reported will be reviewed by the sponsor in bulk (e.g. as listed in TMG reports).

The DMC will periodically review unblinded safety data for each treatment group separately to determine patterns and trends of events, or to identify safety issues that would not be apparent on an individual case basis.

The TSC will periodically review blinded, pooled safety data and liaise with the DMC regarding safety issues.

# 9.4.2. Ongoing events

Some SAEs/SARs/SUSARs may be ongoing at the time of initial reporting.

It is the PI's (or medical delegate's) responsibility that all SAEs/SARs/SUSARs are followed up until the final outcome is reached or up to the end of the study visit at week 35 postrandomisation. There is no mandatory requirement regarding the frequency which follow-up reports should be submitted; however, follow-up information should be entered into the eCRF as soon as the PI (or medical delegate) becomes aware of the outcome.

Ongoing SAEs/SARs/SUSARs at the end of the trial will be followed up by the participant's GP and/or the routine clinical care team until discharge.

#### 9.4.3. Notification of deaths

Irrespective of whether the death is related to the intervention or if it is unrelated, all deaths occurring during the safety reporting period must be reported to ExeCTU and the Sponsor within 24 hours of the PI or research team becoming aware of the event. This will be reported by completing an 'SAE' eCRF and 'Death' eCRF in REDCap.

# 9.4.4. Expedited reporting of SUSARs

If a SUSAR is reported by a site, the Sponsor will coordinate onward reporting to the REC and the MHRA (required within 7 calendar days of receipt of the initial report for fatal/life-threatening events or 15 calendar days of receipt of the initial report for non-fatal/non-life-threatening events)

All other recruiting sites will be informed of the SUSAR by ExeCTU.

#### 9.5. Responsibilities

The CI is responsible for oversight of the safety of participants in the trial, including an ongoing review of the risk/benefit. They will review SAEs causality using their medical judgement and review all SARs for expectedness using the RSI in a timely manner.

The CI (or delegate) will review and confirm the Medical Dictionary for Regulatory Activities (MedDRA) coding assigned by the team at ExeCTU to all reportable safety events.

#### 9.6. Pregnancy reporting

In the event of a pregnancy being reported by a female participant, this must be reported using an ExeCTU 'Pregnancy' eCRF within 24 hours of learning of its occurrence. All pregnancies from randomisation until Week 35 End of Study telephone follow up should be reported. Please note, the completion of the pregnancy eCRF is only required to if a trial participant is pregnant; notification is not required if a participant's partner becomes pregnant.

If a pregnancy is reported during the intervention period, the pregnant participant should be unblinded (see blinding section 7.7) and their clinical management directed by the local PI. Pregnant participants should continue to complete trial follow-up visits unless they withdraw consent. No additional trial follow-up is required for participants who become pregnant during the trial. Due to the minor teratogenic risk of prednisolone, pregnancy outcomes will not be collected for this trial. The British National Formulary states that the benefit of treatment with corticosteroids during pregnancy outweighs the risk (https://bnf.nice.org.uk/drugs/prednisolone).

Pregnancy is not considered an AE unless a negative or consequential outcome is recorded for the mother or child/foetus. If the outcome meets the protocol definition of serious, a serious adverse event eCRF must be completed (see pharmacovigilance section 9).

#### 9.7. Overdose

As per the SmPC for prednisolone, reports of acute toxicity and/or deaths following overdose with glucocorticoids are rare and no specific antidote is available. Treatment should be supportive and guided by symptoms.

All participants that have taken an overdose of IMP should be treated as though they are on the active treatment. Participants should be monitored as per local standard of care practice.

The risk of overdose in the trial has been assessed by the CI as part of the detailed risk assessment.

Any overdose resulting in attendance to A&E or considered significant as assessed by treating clinician must be reported on the 'Non-Compliance' form). If an overdose results in adverse events that meet the protocol definition of serious, a serious adverse event eCRF must be completed in REDCap *in addition* to the 'Non-Compliance' form (see pharmacovigilance section 9).

